Based on this hypothesis, we already investigated the prognostic significance of peripheral blood immune cell counts in HR+/HER2- aBC patients treated with ET+CDK4/6i. 42 In fact, although the main mechanism of CDK4/6i-mediated anticancer activity consists in cell autonomous anticancer effects, preclinical evidence indicates the CDK4/6i ability to stimulate antitumor immunity. To preliminary investigate if peripheral blood immune cell counts or composite immune parameters, as evaluated at baseline or during CDK4/6i therapy, are associated with efficacy of any-line ET+CDK4/6i, we performed an analysis in 638 HR+/HER2- aBC patients treated in six Italian centers. In this study (PALMARES study), we investigated if baseline or ontreatment peripheral blood immune cells, such as lymphocytes, neutrophils, platelets or monocytes, or the composite scores neutrophil-to-lymphocyte ratio (NLR), platelet-to-lymphocyte ratio (PLR), monocyte-tolymphocyte ratio (MLR) or the Pan-Immune Inflammatory Value (PIV), are associated with patient PFS. Peripheral blood immune cell values were collected at baseline (T0), 2 weeks after treatment initiation (T1) and before fourth cycle initiation, approximately 12 weeks after treatment initiation (T2). We used Random Forest models to select clinically relevant covariates (line of therapy for advanced disease, ECOG PS, presence of liver metastases, number of metastatic sites, patient age, disease-free interval (DFI), percentage of Ki-67-positive cells in primary tumor specimens and presence of ER expression in primary tumor specimens) to adjust the role of peripheral blood immune cells in multivariable cox models. Median patient age in this cohort of patients was 61 years (IQR: 52-70 years). The majority of patients were postmenopausal (n=530; 83.1%), had an ECOG PS of 0 (n=464, 72.8%) and were treated with palbociclib (n=529; 82.9%). Approximately half of enrolled patients received CDK4/6i in the first-line setting (n=335; 52.5%) and had visceral disease (n=334; 52.4%). Among all the considered peripheral blood immune variables (neutrophils, platelets, lymphocytes and monocytes, the NLR, the PLR, the MLR and also the PIV), only baseline lymphocyte values and their precocious modulation (i.e. after 2 weeks of treatment), were independently associated with patient PFS.42

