Interestingly, we found that patients with higher baseline lymphocyte counts and undergoing a lower ontreatment reduction of lymphocytes had significantly longer PFS when compared to patients with lower baseline lymphocytes and undergoing a higher decrease of lymphocyte counts [median PFS 21.4 vs. 11 months, respectively; adjusted hazard ratio (aHR): 0.82; 95% CI 0.73-0.93; p=0.0037]. For the first time, these results underlie the prognostic significance of blood lymphocytes in HR+/HER2- aBC patients treated with CDK4/6 inhibitors. ⁴²

Since the majority of HR+/HER2- aBC patients nowadays receive CDK4/6i in the first-line treatment setting, we performed a sub-analysis, in which we evaluated the association of baseline lymphocyte count (L_t0) and its precocious modulation (L_r1) with the PFS of patients treated with CDK4/6i in the first-line setting (n=335; 52.5%). Multivariable analysis revealed an independent and statistically significant association between higher L_r1 and reduced risk of disease progression; on the other hand, L_t0 was not associated with patient PFS. In this model, a higher DFI was associated with better PFS, while a higher number of metastatic sites, as well as higher ECOG PS, were associated with significantly worse PFS. We also adjusted the prognostic role of L_r1 for NLR_t0 in this patient subset. Of note, L_r1 was independently associated with patient PFS (HR: 0.83; 95% CI 0.71-0.99; p=0.0325), while the NLR_t0 was not (HR: 1.08; 95% CI 0.86-1.35 (p=0.5085). Together, these data confirm an independent prognostic role of the precocious modulation of peripheral blood lymphocytes also in the first-line setting. 42

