we conducted a subanalysis on the PALMARES study cohort treated with first-line CDK4/6i plus ET. HER2 status was available for 428 patients in the study cohort. We found that patients with HR+/HER2-low aBC had significantly worse PFS (mPFS 23.6 months vs. 32.3 months; p=0.014) and OS (mOS: 48.7 vs 58.3 months; p=0.029) when compared to patients with HER2-0 aBC. Multivariable analysis confirmed an independent association between HER2-low status and worse PFS (aHR 1.42; 95% CI:1.07-1.89; p=0.016) and OS (aHR: 1.64; 95% CI: 1.08-2.48; p=0.02).⁴⁸ However, another large study conducted by Mouabbi J. et al investigated the prognostic role of HER2 status in 1649 HR+/HER2- aBC patients treated with ET in combination with different targeted therapies (CDK4/6i, everolimus or alpelisib). In the sub-cohort of 919 patients treated with CDK4/6i plus ET, there were no statistically significant differences between patients with HER2-low and HER2-0 aBC in terms of PFS (13.0 vs 11.6 months, p=0.273) and OS (32.4 vs 31.2 months, p=0.222).⁴⁹ The reported discrepancies among published studies, in addition to the increased value of the HER2-low status in the treatment of HR+/HER2- aBC, laid the foundations for further investigations on this potentially useful and easy-to-access biomarker.

To summarize, our previous preliminary results, together with available literature, demonstrated that some biomarkers already available in clinical practice could be potentially used to distinguish different prognostic classes of HR+/HER2- aBC patients treated with first-line ET+CDK4/6i. However, larger studies are necessary to confirm available results and finally implement in clinical practice novel treatment biomarkers.

Differences between the three CDK4/6i drugs in combination with ET and their impact on efficacy

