- To test the association between blood lymphocyte counts at baseline, or their precocious ontreatment modifications (T1: 2 weeks after treatment initiation, and T2: before fourth cycle initiation, approximately 12 weeks after treatment initiation) and rwPFS, TTNT-D, TTC-D and OS of HR+/HER2- patients treated with first-line ET plus CDK4/6i;
- To evaluate the association between peripheral blood crude cell counts, namely whole blood cells, neutrophils, monocytes and platelets, as evaluated at baseline and as precocious on-treatment modifications, and patient rwPFS, TTNT-D, TTC-D and OS;
- To evaluate the association between baseline composite parameters, such as the Neutrophil-to-Lymphocyte ratio (NLR), the platelet-to-lymphocyte ratio (PLR), the monocyte-to-lymphocyte ratio (MLR), or the Pan-Immune Inflammation Value (PIV), and patient PFS;
- To evaluate the association between precocious on-treatment modifications (i.e., 2 weeks and ∼12 weeks after treatment initiation) of NLR, PLR, MLR and PIV, and patient PFS;
- To evaluate the association between HER2 status (HER2-low vs. HER2-0; HER2 2+ with negative ISH vs. HER2 1+ vs. HER2-0) in the primary tumor and rwPFS, TTNT-D, TTC-D and OS;
- To evaluate the association between HER2 status (HER2-low vs. HER2-0; HER2 2+ with negative ISH vs. HER2 1+ vs. HER2-0) in one metastatic site (subjected to biopsy before CDK 4/6 inhibitor initiation), and rwPFS, TTNT-D, TTC-D and OS;
- To explore pattern of progression of HR+/HER2- aBC after ET plus CDK4/6i treatment;
- To test the effect on rwPFS, TTNT-D, TTC-D and OS of mastectomy in patients with *de novo* HR+/HER2- aBC.

Study Population

Inclusion criteria:

- Pre- and Post-menopausal patient (woman OR man)
- Age≥18 years
- Diagnosis of aBC. HR+/HER2- aBC, as defined as at least 1% estrogen receptor (ER) and/or progesterone receptor (PgR) positivity at IHC. HER2 negativity is defined on the basis of an IHC score of 0, 1+, or 2+ with absence of gene amplification at in situ hybridization (ISH) analyses.
- Have received or are candidate to receive treatment with palbociclib, ribociclib or abemaciclib in combination with endocrine therapy as first-line treatment for HR+/HER2- aBC.

Exclusion criteria:

- Less than 3 months of follow up from the CDK4/6i start to the date of data cut-off;
- Have received CDK4/6i as monotherapy;
- Have received CDK4/6i as adjuvant treatment for localized disease.

Data collection

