Clinical real world data will be collected by centers in ad hoc document in .xlsx format. At pre-specified data cut-off (see sections below), data collected will be shared with the Sponsor for data analyses. Investigators at study centers could be required to modify data in case of data inconsistencies encountered during data analyses.

All consecutive HR+ HER2- aBC patients treated with first-line ET plus CDK 4/6i as per clinical practice in the time interval between January 2017 and December 2030 will be enrolled retrospectively and prospectively. Data will be collected in a continuous manner and will be shared with the Sponsor center on an annual basis, at pre-specified data cut-offs. Data cut-offs will occur annually, at certain cutoffs falling on 1st January of each year. Taking into account the time interval and the centers involved, approximately 2000 patients will be included at the first data cut-off of 1st January 2024. Those patients who have already concluded the treatment at the time of study inclusion will be evaluated for clinical outcomes (i.e. PFS, OS) and biological parameters of interest will be retrospectively collected. Patients who are still receiving ET plus CDK4/6i at the time of inclusion in the study will be evaluated for the same variables until the end of the study. At the time of data collection and analysis, these patients will be censored for the events of interest (e.g. progression, death) if these events have not occurred yet.

[figure not shown]

Figure 2. PALMARES-2 study expected timeline and enrollment. EC: ethical committee; pts: patients.

Medical images collection and sharing

The medical images, collected within the timeframe specified in the appropriate section (see section "Medical images sub-study"), will be collected locally in the individual centers, pseudonymised and uploaded to an ad hoc secure sharepoint. A folder will be set up for each individual center participating in this sub-study, so that only the center uploading the images and the Sponsor center itself will be able to access them.

Tumor samples collection, storage and shipment

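### PALMARES-2's test of early lymphocyte change and HER2-low status may partly reuse the PALMARES patients in whom both were found, because no rule or data field separates them

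*Protocol*

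**What the plan says.** The background section on prognostic biomarkers describes PALMARES as the study team's own work: "we performed an analysis in 638 HR+/HER2- aBC patients treated in six Italian centers". Of these, 335 (52.5%) were treated first-line. In that subset the protocol reports that "L_r1 was independently associated with patient PFS (HR: 0.83; 95% CI 0.71-0.99; p=0.0325", whereas "L_t0 was not associated with patient PFS".

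For the HER2 sub-analysis of first-line patients it reports that "HER2 status was available for 428 patients in the study cohort". HER2-low status was associated with worse PFS (aHR 1.42, 95% CI 1.07–1.89, p=0.016) and worse OS (aHR 1.64, 95% CI 1.08–2.48, p=0.02). The same section cites a study with 919 CDK4/6i patients that found no such difference, and concludes that "larger studies are necessary to confirm available results and finally implement in clinical practice novel treatment biomarkers".

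The secondary objectives of the RWD sub-study then include both associations. Under Clinical data collection and management, enrolment takes in "All consecutive HR+ HER2- aBC patients treated with first-line ET plus CDK 4/6i as per clinical practice in the time interval between January 2017" to December 2030, including patients who have already finished treatment. Study duration gives January 2016 as the start instead.

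The RWD exclusion criteria are three: less than 3 months of follow-up, CDK4/6i monotherapy, and "Have received CDK4/6i as adjuvant treatment for localized disease". None concerns PALMARES. The RWD list of data items has no field for earlier study membership, and the identifier under Data protection procedures is issued for this study with no stated link to PALMARES.

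**The concern.** A hypothesis found in one set of patients is confirmed only by patients who did not generate it. If first-line PALMARES patients are collected again, their significant result enters the new test as a fixed contribution. The p<0.05 rule in Statistical methods then no longer has a 5% error rate, and the hazard ratio is pulled toward the earlier value.

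This matters most for HER2-low status, where the protocol itself cites conflicting evidence and wants the question settled before the marker reaches practice.

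**Working it through.** **Inputs.** Earlier results and sizes (638, 335, 428) come from the background section on prognostic biomarkers. About 2000 patients at the first cut-off comes from Clinical data collection and management. The planned 3258 patients come from Statistical design. Two-sided 0.05 comes from Statistical methods. The 3258 is used only as a denominator, so nothing here depends on how it was derived.

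**1. Reproduce the earlier results.** SE = ln(upper/lower)/(2×1.96), z = ln(HR)/SE.

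- HER2-low PFS: SE = ln(1.89/1.07)/3.92 = 0.145, z = 2.42, p = 0.016, as stated.
- HER2-low OS: SE = ln(2.48/1.08)/3.92 = 0.212, z = 2.33, p = 0.020, as stated.
- Early lymphocyte change: SE = ln(0.99/0.71)/3.92 = 0.085, z = −2.20, p = 0.028. The stated 0.0325 is consistent with rounded limits.

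Below, |z| is taken from the stated p-values: 2.41, 2.33 and 2.14.

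**2. Who could re-enter.** Later-line PALMARES patients (638 − 335 = 303) are kept out by the first-line criterion. The ceilings are therefore 335 for lymphocytes and 428 for HER2. The second is uncertain: 428 patients in a first-line sub-analysis exceeds the 335 first-line patients reported for the same cohort.

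Maximum shares: 428/2000 = 21.4%, 428/3258 = 13.1%, 335/2000 = 16.8%, 335/3258 = 10.3%.

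**3. Chance of p<0.05 with no effect in new patients.** Let k be the ceiling, r the fraction of it that re-enters, N the total, and w = r·k/N the share of information (assumed proportional to patients). The pooled Z is normal with mean √(w·r)·z and variance 1 − w·r. With r = 1 this is √w·z plus √(1−w) times a standard normal. With r = 0.5 it allows for a random half carrying only part of the earlier z plus its own sampling error.

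Example, HER2-low PFS, N = 2000:

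- r = 1: w = 0.214, mean = 0.463×2.41 = 1.11, SD = √0.786 = 0.887, P(|Z|>1.96) = 17.0%.
- r = 0.5: w = 0.107, mean = √0.0535×2.41 = 0.557, SD = √0.9465 = 0.973, P = 8%.

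| Marker, outcome | Full, N=2000 | Full, N=3258 | Half, N=2000 | Half, N=3258 |
|---|---|---|---|---|
| HER2-low, PFS | 17.0% | 12.3% | 8% | 7% |
| HER2-low, OS | 16.0% | 11.7% | 8% | 7% |
| Early lymphocyte change, PFS | 11.8% | 9.2% | 7% | 6% |

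With no overlap every entry is 5%. With full overlap nearly all of the probability lies in the original direction, where the nominal rate is 2.5%.

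**4. Shift in the estimate.** The expected pooled HR with no effect in new patients is HR^w. For HER2-low PFS this is exp(0.214×ln 1.42) = 1.08 at 2000 and exp(0.131×ln 1.42) = 1.05 at 3258. For early lymphocyte change it is 0.97 and 0.98.

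**5. Sensitivity.**

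- If only 335 of the 428 HER2 patients can re-enter (r = 335/428 = 0.783), HER2-low PFS gives 12.3% and 9.5%, and OS 11.7% and 9.1%.
- If longer follow-up gave the earlier patients 30–40% of the information (r = 1, w = 0.3–0.4), HER2-low PFS would rise to 22–29% and early lymphocyte change to 17–22%.

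**The case against.** The strongest reply is that overlap is not shown. The protocol gives neither the accrual dates nor the names of the six PALMARES centres, and it states no overlap. A reader might infer that PALMARES patients are certainly counted twice, but the documents support only that they may be. The inference is still strong: the same team, consecutive retrospective enrolment from 2016 or 2017, and PALMARES publications dated 2023. Whatever the extent, the protocol has no means of measuring it.

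A second reply is that a separate analysis may be planned in a statistical analysis plan that is not shown. That is fair, and no claim is made that none exists. But eligibility and data items are fixed here, and an analysis plan cannot set apart patients whom the data file does not identify.

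Third, these are two among many secondary objectives, and the call for larger studies is not a promise of independent replication. This limits the weight of the point but does not remove it, since the protocol cites these findings as the reason for further study.

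Fourth, one might extend the concern to every blood-count and HER2 objective. The documents do not support that. Baseline lymphocytes were not associated with PFS first-line, and the composite scores were not independently associated in the whole cohort. No earlier result is reported for three-level HER2, TTNT-D or TTC-D. These have no significant finding to carry forward.

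Finally, the calculation carries the earlier z over unchanged, although PALMARES-2 uses rwPFS and updated follow-up. This stands as a limit on precision.

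**Conclusion.** The point holds in a limited form. For early lymphocyte change (PFS) and HER2-low versus HER2-0 (PFS, OS), PALMARES-2 as written would not guarantee an independent test, because it can include the discovery patients without identifying them. The chance of a significant result with no effect in new patients is about 9–17% with full overlap and about 6–8% with half overlap, against 5%. The shift in the hazard ratio is modest, to about 1.08 at most for HER2-low PFS in the main calculation.

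These figures assume that information is proportional to patients, that the earlier z carries over, and that the ceilings are 335 and 428, the latter in doubt. The true overlap is unknown. A reader might also infer that the primary result is compromised. It is not: the OS comparisons between drugs were not derived from these PALMARES findings.

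**What to change.** Add a yes/no field 'analysed in PALMARES' to the RWD data file, filled by the sponsor from its earlier dataset. State in the protocol that any claim of confirmation for early lymphocyte change (PFS) and for HER2-low versus HER2-0 (PFS, OS) rests on patients not in PALMARES. Report the full cohort as a secondary pooled estimate, and report the number that overlap. Eligibility need not change, so the consecutive, population-based design is kept, and the other biomarker objectives can use the full cohort.

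Two clarifications would help: reconcile the January 2016 and January 2017 starts, since they affect how many could overlap, and explain how 428 HER2 patients relate to 335 first-line patients.

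The cost is one data field and a smaller confirmatory set for these two markers: at most 428 of 2000 (about 21%) at the first cut-off, or 428 of 3258 (about 13%) at the planned size.
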